8 EFFICACY ANALYSES

Because the majority of PBO subjects will be switched to CZP treatment at or after Week 16, all statistical comparisons between CZP and PBO will be limited to the time period through Week 16 for subjects with moderate to severe chronic plaque PSO. After Week 16, data will be summarized using descriptive statistics only.

8.1 Statistical analysis of the primary efficacy variable(s)

8.1.1 Derivations of primary efficacy variable(s)

The primary efficacy variable for subjects with moderate to severe chronic plaque PSO is the PASI75 at Week 16. The PASI is the most commonly used and validated assessment for grading the severity and extent of the disease.

The PASI score is calculated as follows:

The percent area of involvement (BSA%) is estimated across 4 body areas: head (h) (10% of a person's skin), arms (a) (20%), trunk (t) (30%), legs (l) (40%).

For each section, the percent of area of skin affected (A), is estimated and then transformed into a grade from 0 to 6:

- Grade 0 none
- Grade 1: <10% of involved area affected
- Grade 2: 10% to <30% of involved area affected
- Grade 3: 30% to <50% of involved area affected
- Grade 4: 50% to <70% of involved area affected
- Grade 5: 70% to <90% of involved area affected
- Grade 6: 90% to 100% of involved area affected

Within each section, the severity is estimated by 3 clinical signs: redness (R), thickness (T) and scaling (S). Severity is measured on a scale from 0 to 4 (0 = none and 4 = very marked).

The PASI is a measure of the average redness, thickness, and scaling of the psoriatic skin lesions, multiplied by the involved psoriasis area score of the respective section, and weighted by the percentage of the person's affected skin for the respective section. The following formula is used to calculate the PASI:

$$\text{PASI} = 0.1 \times (\text{Rh} + \text{Th} + \text{Sh}) \times \text{Ah} + 0.2 \times (\text{Ra} + \text{Ta} + \text{Sa}) \times \text{Aa} + 0.3 \times (\text{Rt} + \text{Tt} + \text{St}) \times \text{At} \\ + 0.4 \times (\text{Rl} + \text{Tl} + \text{Sl}) \times \text{Al}$$

The PASI ranges from 0 to 72 with a higher score indicating increased disease.

If a subject is missing 1 or 2 severity measurements for a certain region, the average of the remaining severity measurement(s) within that region will be utilized to substitute for the missing severity measurement(s) in that region. If the area of affected skin and/or all severity measurements for up to 2 regions are missing, then the missing $(\text{R} + \text{T} + \text{S}) \times \text{A}$ for a region will be substituted by the average of the available $(\text{R} + \text{T} + \text{S}) \times \text{A}$. Otherwise, the PASI will be set to missing.

The PASI75 response is based on at least 75% improvement from Baseline in the PASI score.

The % improvement in PASI scores from Baseline will be computed as:

$$\% \text{ improvement from Baseline} \\ = 100 \times (\text{Baseline PASI} - \text{Observed PASI}) / (\text{Baseline PASI})$$

If a subject has experienced an improvement, this measure will be positive. If a subject has experienced a worsening in their condition, this measure will be negative.

The categorical variable PASI75 is defined to be equal to 1 for % improvement from Baseline in PASI scores of 75% or greater and 0 for less than 75%. The classification of subjects as responder or non-responder is based on this definition: 1 = responder, 0 = non-responder.

Similarly, the PASI50, PASI75, PASI90 and PASI100 responses are equal to 1 for subjects with at least 50%, 75%, 90%, and 100% improvement.

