9.1 Psoriasis Area Severity Index (PASI)

The PASI is the most commonly used and validated assessment for grading the severity of PSO in clinical studies (Feldman, 2004). The PASI quantifies the severity and extent of the disease and weighs these with the percentage of BSA involvement.

The percent area of involvement (BSA%) is estimated across 4 body areas; head, upper limbs, trunk, and lower limbs and then transferred into a grade (Table 9–1).

The Investigator assesses the average redness, thickness, and scaliness of lesions in each body area (each on a 5-point scale); 0=none, 1=slight, 2=moderate, 3=marked, and 4=very marked.

The PASI score ranges from 0 to 72 with a higher score indicating increased disease severity.

Table 9–1: Body areas for calculation of percent BSA for PASI

Body area	Details of area	BSA	Degree of involvement of body area ^a
Head	Face, back of head	10%	0 to 6
Upper limbs	Left, right, upper lower, flexor surface, extensor surface	20%	0 to 6
Trunk	Front, back, groin	30%	0 to 6
Lower limbs	Left, right, upper lower, flexor surface, extensor surface, including buttocks	40%	0 to 6
Total		100%	

BSA=body surface area; PASI=Psoriasis Area and Severity Index

^a Where 0=none; 1=1% to <10% affected, 2=10% to <30% affected, 3=30% to <50% affected, 4=50% to <70% affected, 5=70% to <90% affected, 6=90% to 100% affected

The PASI50, PASI75, PASI90, and PASI100 responses are based on at least 50%, 75%, 90%, and 100% improvement in the PASI score.

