8.1.2 Primary analysis of the primary efficacy variable

The primary analysis for the PASI75 response at Week 16 will be based on a logistic regression model for the FAS which will include fixed effects for treatment group and prior biologic exposure (yes/no). Prior biologic exposure was selected as a fixed effect in the logistic regression model as it is a stratification variable for randomization and because it may have an impact on efficacy. The odds ratio, associated confidence interval, and p-value

will be presented. If convergence is not obtained due to having only or no responders in one or more treatment groups, then an exact logistic regression will be applied and odds ratio, associated exact confidence interval, and exact p-value will be determined. If the logistic regression model is unable to converge, then prior biologic exposure may be dropped from the model to facilitate convergence. This model is used when the sample size is too small for a regular logistic regression or when some of the cells formed by the outcome and categorical predictor variable have no observation.

The Markov Chain Monte Carlo (MCMC) method for multiple imputation will be used to account for missing values in the primary analysis of PASI75 at Week 16. The multiple imputation procedure for PASI75 will be based on the actual PASI score.

For derivation of PASI75 response, no rounding will be performed. That is, the imputed Week 16 PASI value will be compared directly to the observed Baseline value to determine whether or not a reduction of at least 75% was achieved.

Each CZP dose will be compared against PBO to establish superiority over PBO and will be tested sequentially at an alpha of 0.025 as outlined in Section 4.5.

Multiple imputation and the subsequent analysis will involve the 3 tasks described below:

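### The SAP's PASI missing-item rule has no exception for a region with area grade 0, so if severities are left blank in clear skin, a known zero is averaged over or PASI becomes missing

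*SAP*

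**What the plan says.** SAP 8.1.1 computes PASI as the sum over head, arms, trunk and legs, with weights 0.1, 0.2, 0.3 and 0.4, of (R+T+S) x A. R, T and S are the three severity scores and A is the area grade, 0 for no involvement up to 6.

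Missing items are handled at two levels:
- If one or two severities are missing in a region, the remaining ones in that region are averaged.
- "If the area of affected skin and/or all severity measurements for up to 2 regions are missing", the region's product "will be substituted by the average of the available" products. Beyond that, "Otherwise, the PASI will be set to missing".

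On severity, the SAP states: "Severity is measured on a scale from 0 to 4 (0 = none and 4 = very marked". Protocol 9.1 uses the same 0 to 4 scale and describes the rating this way: "The Investigator assesses the average redness, thickness, and scaliness of lesions in each body area". Neither document says what to enter for severity in a region without lesions.

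On use of the score: "The PASI75 response is based on at least 75% improvement from Baseline in the PASI score". For a missing Week 16 PASI, SAP 8.1.2 states: "The Markov Chain Monte Carlo (MCMC) method for multiple imputation will be used to account for missing values". The sensitivity analysis in SAP 8.1.3 counts a missing Week 16 response as non-response.

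**The concern.** The trigger is joined by and/or, so it covers a region whose area is recorded and whose three severities are all blank. If that recorded area is 0, the product is already determined: anything times 0 is 0. The rule nevertheless fills it with an average taken from the other regions or, with three or four such regions, discards the whole score.

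Blank severities in clear skin are plausible because severity is defined on lesions, and a cleared region has none to rate. They would arise mostly in subjects who are clearing, that is, mostly on CZP.

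PASI75 at Week 16 is the primary endpoint and PASI90 at Week 16 is in the alpha-controlled sequence (SAP 4.5). PASI100 is exposed most directly, since complete clearance is the case that would be lost. Earlier PASI scores are predictors in the imputation model of SAP 8.1.2, so a mis-scored earlier visit would carry forward too.

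**Working it through.** **The plan's own figure.** With all severities at 4 (sum 12) and all areas at 6, the formula gives (0.1 + 0.2 + 0.3 + 0.4) x 12 x 6 = 72. This agrees with "The PASI ranges from 0 to 72 with a higher score indicating increased disease".

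**The item-level rule is harmless here.** If only one or two severities are blank and A = 0, the averaged severities are multiplied by 0 and the product stays 0. The problem arises only when all three are blank.

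**Error formula.** For one or two clear regions with blank severities, literal PASI minus true PASI = (sum of the weights of the blank regions) x (mean of the available products).

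**Constructed records** (assumed scores; clear regions have A = 0 and blank severities):

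| Record | Available products | True PASI | Literal PASI |
|---|---|---|---|
| 1. Head and trunk clear | arms 3, legs 6 | 0.2 x 3 + 0.4 x 6 = 3.0 | 3.0 + 0.4 x 4.5 = 4.8 |
| 2. Head and arms clear | trunk 3, legs 3 | 0.3 x 3 + 0.4 x 3 = 2.1 | 2.1 + 0.3 x 3 = 3.0 |
| 3. Head and trunk clear | arms 6, legs 8 | 0.2 x 6 + 0.4 x 8 = 4.4 | 4.4 + 0.4 x 7 = 7.2 |
| 4. Head, arms and trunk clear | legs 3 | 0.4 x 3 = 1.2 | missing |
| 5. All clear | none | 0 | missing |

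**When response status changes.** PASI75 requires a score of at most Baseline/4. It is wrongly lost when 4 x true ≤ Baseline < 4 x literal. PASI90 is wrongly lost when 10 x true ≤ Baseline < 10 x literal. Protocol 6.1.2 requires a Baseline PASI of at least 12.

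| Record | PASI75 lost for Baseline | PASI90 lost for Baseline |
|---|---|---|
| 1 | 12 to below 19.2 | 30 to below 48 |
| 2 | never (8.4 to below 12, under the entry minimum) | 21 to below 30 |
| 3 | 17.6 to below 28.8 | 44 to below 72 |

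Spot values:
- Record 1 at Baseline 16: improvement 81.3% true, 70.0% literal. At Baseline 20: 85.0% and 76.0%, so there is no PASI75 change.
- Record 2 at Baseline 24: 91.3% true, 87.5% literal.
- Record 3 at Baseline 21.4: 79.4% true, 66.4% literal.

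For scale, mean Baseline PASI in the Phase 2 retreatment study was 21.89 and 22.99 (Protocol Table 5-3). At those values Record 1 remains a PASI75 responder, while Record 3 does not.

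**If zeros are entered.** With severities recorded as 0/0/0 the rule is never triggered, and literal and true scores agree in every record.

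**The case against.** The strongest reply is that blank severities are nowhere described. Both documents provide a score of 0 for none and have severity assessed in each body area, so a clear region can be recorded as 0/0/0, and the rule then does nothing. Data checks, manual review and monitoring (Protocol 13.2 and 13.3.2) make blanks in the primary instrument less likely. The Week 16 PASI50 decision on escape would also tend to expose a subject with no computable score. This stands as a limit on frequency. It does not correct the rule, because nothing in either document says that zeros must be entered.

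A second reply is that the SAP substitutes a missing product, and a product with A = 0 is arguably not missing. That reading is reasonable. But the trigger is written in terms of missing area or missing severities, not an undetermined product, so a programmer following it literally would substitute.

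A reader might infer more than the documents support:
- *That clear skin will be scored as disease.* This is conditional on blanks, which the documents do not establish.
- *That the substitute comes only from regions still diseased.* The average is over all available regions; a clear region scored with zeros enters it and lowers it.
- *That a cleared subject is lost from the primary analysis.* A missing Week 16 PASI is imputed within treatment arm from Baseline and earlier PASI scores, with negative values set to 0 (SAP 8.1.2), and would usually come out low. Automatic non-response applies only under NRI.
- *That the PASI75 conclusion is in danger.* By Fisher's exact test at 50 versus 25 and two-sided 0.025, power is 99.3% at the assumed 70% versus 15%, and still 94.6% if the CZP rate fell to 60%.

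**Conclusion.** The gap is real but conditional. As written, SAP 8.1.1 gives a wrong PASI for a region with area grade 0 and three blank severities, and no PASI when three or four regions are in that state. Where this occurs, the overstatement was 0.9 to 2.8 points in the constructed records. That is enough to change PASI75 or PASI90 for some Baseline values and not for others.

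The frequency cannot be determined from the documents. It ranges from none, if 0/0/0 is always entered, to every subject with a cleared region. After Baseline the error grows with clearing, so it would mainly lower CZP response rates and the estimated differences from placebo. If the arms did not differ, the same scoring error would apply alike in each, so it does not inflate type I error. The sample size is unaffected.

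It still merits correction, because the derivation of the primary variable should not depend on an unstated data-entry convention.

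**What to change.** Add to SAP 8.1.1, ahead of the missing-item rules: a region with area grade 0, or with all three severities recorded as 0, contributes (R+T+S) x A = 0 whatever else is missing in that region. Then restrict the averaging and set-to-missing rules to regions whose product is still undetermined, and count only those regions towards the limit of two.

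The cost is one or two sentences and a line of derivation code. No new data are needed, and if zeros are always entered in clear regions no result changes.

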8.1.2 Primary analysis of the primary efficacy variable

The primary analysis for the PASI75 response at Week 16 will be based on a logistic regression model for the FAS which will include fixed effects for treatment group and prior biologic exposure (yes/no). Prior biologic exposure was selected as a fixed effect in the logistic regression model as it is a stratification variable for randomization and because it may have an impact on efficacy. The odds ratio, associated confidence interval, and p-value

will be presented. If convergence is not obtained due to having only or no responders in one or more treatment groups, then an exact logistic regression will be applied and odds ratio, associated exact confidence interval, and exact p-value will be determined. If the logistic regression model is unable to converge, then prior biologic exposure may be dropped from the model to facilitate convergence. This model is used when the sample size is too small for a regular logistic regression or when some of the cells formed by the outcome and categorical predictor variable have no observation.

The Markov Chain Monte Carlo (MCMC) method for multiple imputation will be used to account for missing values in the primary analysis of PASI75 at Week 16. The multiple imputation procedure for PASI75 will be based on the actual PASI score.

For derivation of PASI75 response, no rounding will be performed. That is, the imputed Week 16 PASI value will be compared directly to the observed Baseline value to determine whether or not a reduction of at least 75% was achieved.

Each CZP dose will be compared against PBO to establish superiority over PBO and will be tested sequentially at an alpha of 0.025 as outlined in Section 4.5.

Multiple imputation and the subsequent analysis will involve the 3 tasks described below:

1. Create a data set, one for each treatment group, of subjects with observed values and those needing estimation by MCMC. The missing PASI values in each data set will be filled in using the MCMC method with a total of 75 sets of imputation being performed. The seed used for these imputations will be 958 (Note: All other multiple imputation procedures described in this SAP will use this same seed as well). The procedure will sequentially estimate an imputation model for the PASI score at each post-Baseline visit (up to Week 16) where PASI is collected, with prior biologic exposure, and Baseline score as predictors. Note that PASI scores at earlier visits will also be used as predictors for the model of PASI at later visits. The resulting data sets for each treatment arm will be combined into one complete data set based on each of the 75 imputations.

Note: If one treatment group is complete, so without any missing values, then this treatment group is excluded from MCMC imputation and the observed data will be duplicated 75 times and rejoined to the imputed data set.

Note: The imputation model based on the MCMC method will only allow continuous variables as predictors. Therefore, prior biologic exposure will be re-coded as indicator variables (with values of 0 or 1). Because prior biologic exposure has just 2 levels, only one indicator variable will be needed.

2. For each complete imputed data set, the dichotomous responder rate based on the PASI scores will be computed. Each complete imputed data set will then be analyzed based on a logistic regression model with factors of treatment group and prior biologic exposure (yes/no).

Note: For derivation of PASI75 response, the imputed PASI value will be compared directly to the observed Baseline PASI value to determine whether or not a reduction of at least 75% was achieved. If values outside of the pre-defined range of values for PASI (0-72) are imputed, they will be cut off as appropriate after the multiple imputation procedure but before deriving the responder variables. For example an imputed PASI value of -0.5 would be changed to 0 before deriving the PASI75 responder variable.

3. The Week 16 results from the logistic regression analysis of each of the 75 imputed data sets will be combined into a single inference using SAS PROC MIANALYZE.

Some key points to consider relative to the calculation of the odds ratios and corresponding confidence intervals are noted below:

As the estimates of the odds ratios from the logistic regression model follow a log-normal distribution, a log transformation is needed to normalize these estimates since the procedures for combining results from multiple imputed datasets are based on the assumption that the statistics estimated from each imputed dataset are normally distributed. Therefore, the log of the odds ratio estimates from the logistic regression model will need to be used when combining into a single inference (the PROC MIANALYZE step). Additionally, the standard errors for the odds ratios are transformed as follows:

$$[\log(\text{UCL}) - \log(\text{LCL})] / (2 * Z_{\alpha/2})$$

where UCL and LCL are the upper and lower confidence limit, respectively, for the confidence interval of the odds ratio from the logistic regression model, and $Z_{\alpha/2}$ is the relevant critical value from the standard normal distribution (based on $\alpha=0.05$ for a 95% confidence interval and $\alpha=0.025$ for a 97.5% confidence interval).

The PROC MIANALYZE step takes the estimates of the log odds ratio and standard errors for each imputation and combines them to derive a single estimate of the log odds ratio and corresponding standard error. The odds ratio is then estimated by exponentiating the estimate of the log odds ratio. The confidence limits of the odds ratio are then estimated as follows:

$$\text{LCL} = \text{OR} * \exp(-\text{SE} * Z_{\alpha/2})$$

$$\text{UCL} = \text{OR} * \exp(\text{SE} * Z_{\alpha/2})$$

where OR is the back-transformed estimate of the odds ratio just described, SE is the standard error of the log odds ratio derived in PROC MIANALYZE, and $Z_{\alpha/2}$ is the relevant critical value from the standard normal distribution (based on $\alpha=0.05$ for a 95% confidence interval and $\alpha=0.025$ for a 97.5% confidence interval). These calculations will be done such that odds ratios and corresponding confidence intervals are calculated for the odds ratio of each CZP dose versus placebo. Note that the p-values presented in the tables will be the ones provided initially by PROC MIANALYZE and are not impacted by the transformations described above.

In addition to calculating the odds ratio, associated CIs, and p-values for the pairwise comparisons of each CZP treatment group with PBO, the estimated proportion of responders (eg, estimated responder rate) and the difference in the proportion of responders between each CZP treatment group and PBO will be estimated, and 2-sided 95% CIs will be created for each difference. The creation of these estimates will be completed for each CZP treatment group using the process detailed below:

1. Use the logistic regression model to calculate:
 - a. Least squares mean estimates of the log odds of CZP (G_C) and PBO (G_P), as well as their corresponding standard errors (S_C and S_P , respectively)
 - b. Standard error of the least squares mean estimate of the log odds ratio (S_R)
2. Compute estimates for predicted proportions using the following transformations:

$$P_C = \exp(G_C) / (1 + \exp(G_C))$$

$$P_P = \exp(G_P) / (1 + \exp(G_P))$$

The difference in proportions is then given by:

$$D = P_C - P_P$$

3. Estimate the standard error of D by:

$$S_D = \sqrt{P_C^2 (1 - P_C)^2 S_C^2 + P_P^2 (1 - P_P)^2 S_P^2 + P_C (1 - P_C) P_P (1 - P_P) S_R^2 - P_C (1 - P_C) P_P (1 - P_P) (S_C^2 + S_P^2)}$$

The Markov Chain Monte Carlo (MCMC) method for multiple imputation, as previously outlined, will be used to account for missing values of PASI. This method will create multiple complete data sets which may be analyzed with the process described above. An estimate for the difference in proportions, D, and corresponding standard error, SD, will be computed for each complete dataset.

The results from these analyses will be combined into a single 2-sided 95% confidence interval using SAS PROC MIANALYZE.

In cases where one treatment group has either no responders or only responders, exact logistic regression will be used to calculate the odds ratio with its corresponding confidence interval and p-value. The exact logistic regression will include treatment, and prior biologic exposure as in the primary model. The following procedure will be used to obtain these estimates:

1. Obtain the odds ratio and lower 2-sided confidence limit (based on $\alpha=0.05$ for a 95% confidence interval and $\alpha=0.025$ for a 97.5% confidence interval) for each imputation from PROC LOGISTIC using the EXACT statement and ESTIMATE=BOTH option.
2. Take the log of the exact odds ratio for each imputation and calculate $[\log(\text{odds ratio}) - \log(\text{lower/upper CL})] / Z_{\alpha/2}$ for each imputation as the standard error. Note the upper/lower CL will not be used as it is undefined for cases where there are no/only responders in a treatment group.
3. Use PROC MIANALYZE to combine the log odds ratio estimates and standard errors into a single estimate and corresponding standard error.
4. Exponentiate the estimate obtained from the previous step to obtain the odds ratio and calculate the confidence interval as $OR * \exp(\pm (SE * Z_{\alpha/2}))$ where OR is the odds ratio estimate and SE is the combined estimate of the log odds ratio from PROC MIANALYZE.

This method of exact logistic regression will be used for any endpoint in the statistical hierarchy when one treatment group has no responders.

The calculation of responder rates and the differences in proportion of responders is also impacted when at least one treatment group has no/only responders. In this case, the responder rate will be calculated as the simple proportion of responders for each treatment group across all 75 imputed data sets. The difference in proportions between each CZP group and placebo is calculated for each imputation. The standard error of the difference in proportions for a given CZP group versus placebo is then calculated for each imputation. The standard error is calculated as:

$$\sqrt{\hat{p}(1 - \hat{p})\left(\frac{1}{n_1} + \frac{1}{n_2}\right)},$$

where

$$\hat{p} = \frac{Y_1 + Y_2}{n_1 + n_2}.$$

Note that Y_1 and Y_2 are the number of responders in the placebo and given CZP group, respectively, while n_1 and n_2 are the total number of subjects in each group, respectively. The estimates for the difference in proportion of responders and the standard error above are passed into PROC MIANALYZE so that the overall difference in proportion of responders and the 95% confidence interval can be calculated.

Some additional considerations in the event that there are no/only responders in a given treatment group are as follows:

- If there are no/only observed responders in any treatment group, then none of the calculations described above will be done and the responder rates will be presented as 0/1 while all other statistics will not be calculated.
- If there are no/only observed responders in two of the groups, then responder rates will be calculated as described above, but the difference in proportions and odds ratio calculations will be done only for PBO and the CZP group with more than 0 responders.
- If there is a case where all imputed data sets are exactly the same, then combined estimates of the standard error cannot be calculated. Therefore, the results will be based on the actual observed data and on the (exact) logistic regression using this data.

